6.2 ADDITIONAL MEASUREMENTS

We will collect additional subjective and objective measurements that will be used to: 1) describe the study population and 2) serve as confounding factors in multivariable analysis of the change in fibroid-related symptoms over time.

6.2.A Pre-Enrollment Assessment, Study Participants

At baseline, we will query women about their general and reproductive health and obtain baseline data on fibroid size, number, and location as outlined in Table 3.

Participant-Reported Baseline Measures	
 • Demographic characteristics (age, race/ethnicity, education) • Medical and surgical history • Reproductive history (including pregnancy and pregnancy outcomes) • Medication use • Complementary and alternative therapy use • Desire for future fertility
Objective Baseline Measures	
 • Weight • Height • Vital signs • Uterine size by trans-vaginal ultrasound

	
 • Fibroid characteristics on ultrasound 
 *Total number *Location of each fibroid * dimensions in mm of each fibroid * dimensions in mm of each ovary *Presence of ovarian cysts and sizes
--	---

7.0 ADVERSE EVENTS

This is the first trial of letrozole monotherapy for >12 weeks among premenopausal women. Therefore, a full range of adverse events will be assessed by using the open ended question “Have you had any changes to your health that impact your ability to perform your normal activities?”. In addition to assessing adverse events monthly during the trial, we will query participants about adverse events 30 days after completing the last dose of medication.

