Estradiol and follicle-stimulating hormone (FSH) levels will be measured at baseline and the end of month 2, 4 and 6. These hormones will detect the development of hypoestrogenism and assess changes in the hypothalamic-pituitary-ovarian axis that regulate normal menstrual function. All blood draws will be performed by certified phlebotomists in the REI practice.

6.1.D Total Cholesterol

Since hyperlipidemia is a rare side effect of letrozole, total cholesterol will be measured at baseline and month 6. All blood draws will be performed by certified phlebotomists in the REI practice. Approximately 5 ml (1 tsp) will be drawn at Baseline and Month 6 for this test.

6.1.E Other Outcomes

Other outcomes related to study intervention and fibroid symptoms will include measures related to:

Treatment Failure: We will ask participants to report any additional fibroid treatments including medical management for fibroid-related symptoms, myomectomy, hysterectomy, uterine artery embolization, MR Guided Focused Ultrasound, endometrial ablation, dilation and curettage, or any new and emerging fibroid treatments.

Adverse Events

This is the first trial of letrozole monotherapy for >12 weeks among premenopausal women. Therefore, a full range of adverse events will be assessed every 2 months for all body systems including known potential side effects such as hot flashes, myalgias, and fatigue as well as unknown side effects that will be identified by using the open ended question "Have you had any changes to your health that impact your ability to perform your normal activities?". In addition to assessing adverse events monthly during the trial, we will query participants about adverse events 30 days after completing the last dose of medication.

Pregnancy and pregnancy outcomes: In this study pregnancy is considered a Serious Adverse Event. Participants will report all known pregnancies while receiving study medication. For each pregnancy, we will query participants about whether the pregnancy resulted in a miscarriage, abortion, or continued pregnancy. For continued pregnancies, we will ask participants to report obstetric outcomes including gestational age at birth, mode of delivery (vaginal or cesarean), and complications (e.g. placenta previa, placental abruption, preeclampsia).

6.1.F Long-term storage of blood

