During blood draws at baseline and month 2, 4, and 6, we will ask participants if they are willing to allow long-term storage of their blood (serum) for future fibroid studies. Participants may decline this long term storage and still participate in the study. Specimens will be stored long-term in the Specimen Bank within the UCSF Reproductive Medicine Lab.

6.1.G Schedule of Outcomes Assessment

Outcomes will be assessed at varying timepoints from Baseline to 6 months (Table 2). In-person study visits will occur prior to randomization at the Baseline Visit (BV), Month 2, Month 4, and Month 6. All other visit data will be collected through mailed or on-line questionnaires, and/or phone interviews.

	BV	Mo 1	2	3	4	5	6	7
Symptom questionnaires	X	X	X	X	X	X	X	
EQ5D questionnaire	X		X		X		X	
Pelvic ultrasound	X		X		X		X	
Hormone levels	X		X		X		X	
Total Cholesterol	X						X	
Adverse event assessment		X	X	X	X	X	X	X
Specimen Storage*	X		X		X		X	
Compensation	\$25		\$25		\$25		\$25	

*Optional

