7.1 Adverse Event Grading Scale

Adverse events will be graded using the NCI Common Terminology Criteria for Adverse Events (CTCAE) and Common Toxicity Criteria (CTC), version 4. Using this system, adverse events are classified as follows:

Grade 1	Mild; asymptomatic or mild symptoms; clinical or diagnostic observations only; intervention not indicated.
Grade 2	Moderate; minimal, local or noninvasive intervention indicated; limiting age-appropriate instrumental activities of daily living
Grade 3	Severe or medically significant but not immediately life-threatening; hospitalization or prolongation of hospitalization indicated; disabling; limiting self care activities of daily living
Grade 4	Life-threatening consequences; urgent intervention indicated.
Grade 5	Death related to Adverse Event

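### The open adverse-event question is limited to changes that affect normal activities, so mild unknown effects are likely to be under-reported, and no pre-dose record of symptomatic side effects is listed

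*Combined protocol and SAP*

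**What the plan says.** **Method.** Section 7.0 notes that letrozole alone has not been trialled beyond 12 weeks in premenopausal women, and on that ground promises broad adverse-event capture. The only instrument it names is the open question "Have you had any changes to your health that impact your ability to perform your normal activities". Section 6.1.E is fuller: "a full range of adverse events will be assessed every 2 months for all body systems including known potential side effects", with hot flashes, myalgias and fatigue as examples. It then turns to "unknown side effects that will be identified by using the open ended question", which is the same restricted question.

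**Grading.** Section 7.1 uses CTCAE. Grade 1 reads "Mild; asymptomatic or mild symptoms; clinical or diagnostic observations only; intervention not indicated". Limitation of activities first appears in the Grade 2 definition.

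**Timing and mode.** Section 6.1.E gives a two-monthly frequency in the sentence quoted above, and then says "In addition to assessing adverse events monthly during the trial". In Table 2 (Section 6.1.G) the row "Adverse event assessment" is blank at the baseline visit and marked at months 1 to 7. In-person visits are at baseline and months 2, 4 and 6. For the rest, "All other visit data will be collected through mailed or on-line questionnaires, and/or phone interviews".

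**Baseline.** Section 6.2.A says "we will query women about their general and reproductive health". Table 3 lists medical and surgical history, medication use and ovarian cysts, among other items. It lists no side-effect symptoms.

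**Use.** Section 3.0 assigns the evaluation of long-term safety to within-group comparisons in Group A over months 1 to 6. Section 4.0 links the Group A data to safety beyond 3 months.

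**The concern.** The purpose and the instrument do not match. A woman with a new but tolerable symptom that does not interfere with her day can truthfully answer no to the open question. Such an event belongs in Grade 1, which the protocol intends to record. Known effects are better protected, because Section 6.1.E assesses them separately. A form built from Section 7.0 alone, however, would lose that protection too.

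The second gap concerns interpretation. Hot flashes, myalgias and fatigue can be present before the first dose. If they are first asked about at month 1, a pre-existing complaint may be recorded as a new event. This matters most in the Group A safety reading, which is made within the group.

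At stake is the description of mild effects and of when they began. That description is one of the products this pilot should hand to the full-scale trial. No efficacy result and no power statement depends on it.

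**Working it through.** The documents state no adverse-event rate or detection target, so there is no planned figure to reproduce. The check is mainly a comparison of sections, with illustrative arithmetic to show scale.

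**1. Route by type of effect**

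| Type of effect | Section 6.1.E | Section 7.0 |
|---|---|---|
| Known | Assessed, with examples, across body systems | Open question only |
| Unknown, affecting activities | Open question | Open question |
| Unknown, not affecting activities | Outside the open question; perhaps caught by the body-systems assessment | Outside the open question |

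The last row is where Grade 1 unknown effects fall. No prompt for them is spelled out in either section.

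**2. Contacts.** Table 2 marks 7 adverse-event contacts per woman (months 1 to 7). Three are in person (months 2, 4, 6) and four may be remote (months 1, 3, 5, 7). With 20 women and no dropout, 20 × 4 = 80 of 20 × 7 = 140 contacts (57%) may be remote. Telephone interviews are allowed, so the number that are self-completed forms, where the printed wording may be the only prompt, lies anywhere from 0 to 80.

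**3. Illustration of lost reports.** Group A has n = 10 (20 women at 1:1, Section 3.0). Let q be the true incidence of a mild unknown effect and c the share of affected women who would report it. Both are assumptions.

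P(at least one report) = 1 − (1 − q·c)^10

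| q | c = 1 | c = 0.5 | c = 0.25 |
|---|---|---|---|
| 10% | 65% | 40% | 22% |
| 20% | 89% | 65% | 40% |
| 30% | 97% | 80% | 54% |

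For q = 20%: 1 − 0.80^10 = 0.893; 1 − 0.90^10 = 0.651; 1 − 0.95^10 = 0.401. Section 10.0 refers to 15 women in Group A, which does not follow from 20 at 1:1. With n = 15 and q = 20%, the first two values are 97% and 79%, so the pattern is the same.

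**4. Illustration of the missing baseline.** Let b be the share of women with a symptom before dosing and f the share of those who report it as new. Both are assumptions. Expected false new cases in Group A = 10·b·f.

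- b = 10%, f = 25%: 10 × 0.10 × 0.25 = 0.25 women
- b = 20%, f = 50%: 10 × 0.20 × 0.50 = 1 woman
- b = 30%, f = 100%: 10 × 0.30 × 1 = 3 women (an extreme)

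**5. Which comparator is available.** Group B follows P P L L P P. Months 1–2 give a randomised placebo comparison in women not yet given study letrozole. In months 3–4 both groups take letrozole. In months 5–6 Group B is on placebo again, but after two months of letrozole.

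**The case against.** The strongest reply is that Section 6.1.E already covers all body systems and gives the three symptoms only as examples, so a competent assessment could pick up mild effects beyond them. The cited adverse event case report form and monitoring charter may say more. The open question asks about changes, so it carries a recalled baseline, and medical history and medication use are recorded before dosing. Monthly contacts help to date onset. In a 20-woman pilot, precision is poor whatever is done: 2 of 10 has a 95% interval of 2.5% to 55.6%, and 0 of 10 has an upper limit of 30.8%.

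Much of this stands, and it limits the point to mild unknown effects and to symptoms. It does not remove it. Section 6.1.E itself assigns unknown effects to the restricted question, Section 7.0 does not repeat the body-systems assessment, and recall is weaker than a pre-dose record.

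Three stronger readings are tempting and are not supported:

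- A reader might infer that Group A has no concurrent control after month 2, so that a symptom baseline is the only way to separate old from new. Group B is on placebo again in months 5–6. Its earlier letrozole weakens that comparison but does not abolish it.
- A reader might infer that side effects have no baseline at all. Total cholesterol, estradiol, FSH and ovarian cysts are all recorded at baseline. Nor does Section 10.0 define a change-from-baseline analysis of adverse events that the blank cell in Table 2 would break.
- A reader might infer that adverse events in Group B will be pooled across its placebo and letrozole months. No document proposes this. Section 8.0 describes only the display to the monitor by study group, and the analysis section is not exhaustive.

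**Conclusion.** The point holds in a limited form. Following the stated wording, mild unknown effects are likely to be under-reported, because the named prompt asks only about changes that interfere with activities while grading begins below that threshold. Sections 6.1.E and 7.0 also differ on method. No pre-dose record of hot flashes, myalgias or fatigue is listed, which makes the Group A safety reading harder to interpret, above all outside months 1–2. In months 1–2, randomisation balances pre-existing symptoms in expectation.

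The likelihood of under-reporting is a judgement, and its size cannot be derived from the documents. The fall from 89% to 65% rests on an assumed 20% incidence and on half the cases going unreported. The figure of 0.25 to 3 misattributed women per 10 rests on assumed values of b and f, and the upper end requires every pre-existing symptom to be reported as new. The gain from changing the plan is a cleaner description of tolerability, not power. It is a worthwhile, inexpensive improvement rather than a flaw that threatens the trial.

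**What to change.** - Remove the activity restriction from the open question, for example by asking simply whether there have been any changes in health. Ask about impact on activities afterwards, as an input to grading.
- Ask the same side-effect checklist (hot flashes, myalgias, fatigue and any other listed items) and an open question at the existing baseline visit and at each scheduled adverse-event contact. The baseline open question should ask about current complaints, since there is no earlier visit from which to report change.
- Align Sections 6.1.E, 6.1.G and 7.0 on method and frequency. The two-monthly and monthly statements may describe visits and remote contacts respectively; if so, say so.
- Reconcile Section 7.2 (adverse-event reports every 4 months) with Section 8.0 (every 3 months).
- If the case report form, manual or charter already does any of this, cite it in the protocol.

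The cost is a few more minutes at baseline, revised form wording, and more mild events to record and grade. No visit, blood draw or scan is added. The baseline record has to be in place before dosing, because it cannot be recovered afterwards.

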7.1 Adverse Event Grading Scale

Adverse events will be graded using the NCI Common Terminology Criteria for Adverse Events (CTCAE) and Common Toxicity Criteria (CTC), version 4. Using this system, adverse events are classified as follows:

Grade 1	Mild; asymptomatic or mild symptoms; clinical or diagnostic observations only; intervention not indicated.
Grade 2	Moderate; minimal, local or noninvasive intervention indicated; limiting age-appropriate instrumental activities of daily living
Grade 3	Severe or medically significant but not immediately life-threatening; hospitalization or prolongation of hospitalization indicated; disabling; limiting self care activities of daily living
Grade 4	Life-threatening consequences; urgent intervention indicated.
Grade 5	Death related to Adverse Event

7.2 Reporting of Adverse Events

Grade 4 or 5 adverse events will be reported to the respective institution’s Institutional Review Board (IRB) and the UCSF Coordinating Center within 24 hours. The UCSF Coordinating Center will notify the study sponsor, the UCSF IRB, and the Data and Safety Monitoring Board (DSMB) Chair within 24 hours of the adverse event. The DSMB will receive a report of all adverse events every 4 months, categorized with the appropriate severity grading. The DSMB report will include details of the adverse event as reported in the Adverse Event Case Report Form.

8.0 DATA AND SAFETY AND MONITORING PLAN

The Data and Safety and Monitoring Board will consist of a single Data Safety Monitor (DSM), an obstetrician/gynecologist with expertise in clinical studies of gynecologic interventions and the conduct of clinical trials.

The DSM will be charged with overseeing participant safety and monitoring the scientific validity of the trial. Prior to initiating the study, the DSM will review and approve the study protocol.

Assessment and Reporting of Adverse Events: The DSM will receive updates on adverse events every 3 months during the study. These will be presented to her by study group in a blinded fashion. All serious adverse events will be reported to the DSM within 24 hours of notification to the investigator.

Assessment and Reporting of Study Conduct: Every 3 months, we will report to [name] updated data on the number of potential participants screened, excluded, and enrolled in the study. We will also report adherence to study visits and medication.

Interim Analysis and Stopping rules: This is a small pilot study of 20 women with a short duration of 6 months. Therefore, the sample size and length of study is not appropriate for an interim analysis. In addition, we do not believe a stopping rule is indicated in this small pilot.

Full details of the DSMB are described in the PLUM DSMB Charter.

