3.0 STUDY OVERVIEW

This is a randomized, blinded, placebo-controlled trial of oral letrozole among 20 premenopausal women with symptomatic uterine fibroids. Participants will be randomly assigned in a 1:1 ratio to either oral letrozole 2.5mg/day for 6 months (Group A) or intermittent dosing with letrozole 2.5mg/day and an identical placebo capsule (Group B). Group B will receive medication dosing as follows: 2 months of placebo, then 2 months daily letrozole 2.5mg/day, then 2 months of placebo (Table 1). This dosing regimen in the two groups will allow for: 1) between group comparisons in month 1 and 2 to assess the efficacy of letrozole compared with a placebo, 2) within-group comparisons in month 3-6 in group B to evaluate the rate of fibroid regrowth after discontinuing letrozole to evaluate the possibility of intermediate dosing and 3) within-group comparisons in group A in month 1-6 to evaluate the safety of long-term letrozole use. This pilot data will be critical for determining the appropriate long-term dosing regimen in a future, larger, full-scale trial of letrozole.

Month	1	2	3	4	5	6
Group A	L	L	L	L	L	L
Group B	P	P	L	L	P	P

We will assess changes in fibroid symptoms, quality of life, and sexual functioning monthly using standardized, validated questionnaires. In addition, at baseline, month 2, 4 and 6, we will assess changes in the following measures:

- 1) fibroid and uterine volume assessed by pelvic ultrasound
- 2) serum follicle stimulating hormone (FSH) and estradiol levels to determine ovarian function

Study participants will be recruited at UCSF. All study data will be stored securely in a HIPAA compliant, secure database monitored by the UC San Francisco Coordinating Center. A data safety and monitoring board will oversee participant safety and protection.

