4.0 STUDY OBJECTIVES

The PLUM study will collect essential preliminary data to guide and inform a future multi-centered, randomized trial of letrozole versus placebo. The 3 primary study goals are:

1. To assess the feasibility of conducting a randomized, placebo-controlled trial of letrozole for premenopausal women with fibroids.
2. To collect pilot data that examines differences in fibroid symptoms, fibroid volume, and hormone levels among premenopausal women who take letrozole compared with a placebo.

These will be between-group analyses in Months 1 and 2 (Group A vs. Group B) that serve as preliminary data on the efficacy of letrozole in a placebo-controlled trial.

3. To collect pilot data that examines changes in fibroid symptoms, fibroid volume, and hormone levels among premenopausal women taking continuous and intermittent letrozole dosing.

These will be within-group analyses as follows: Months 1-6 for Group A, Months 3-6 for Group B. These data will provide preliminary information on the safety of letrozole use beyond 3 months (Group A) and the rate of fibroid regrowth after letrozole is discontinued (Group B).

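### Cumulative adverse-event totals by study group understate the absolute letrozole-placebo difference because Group B switches treatment; section 8.0 should specify tables by coded group and 2-month period

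*Combined protocol and SAP*

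**What the plan says.** Section 8.0 gives one rule for how adverse events are laid out for the single safety monitor: "These will be presented to her by study group in a blinded fashion". On timing it says: "The DSM will receive updates on adverse events every 3 months during the study". Section 7.2 gives a different interval: "The DSMB will receive a report of all adverse events every 4 months, categorized with the appropriate severity grading". It adds: "The DSMB report will include details of the adverse event as reported in the Adverse Event Case Report Form".

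Section 3.0 allocates 20 women 1:1. Group A takes letrozole throughout. For the other arm: "Group B will receive medication dosing as follows: 2 months of placebo, then 2 months daily letrozole 2.5mg/day, then 2 months of placebo".

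Objective 3 in section 4.0 looks to Group A for preliminary safety information beyond 3 months. Section 10.0 describes models for UFS-QOL, hormone levels and fibroid volume, but no adverse-event analysis. Section 8.0 also says that there is no interim analysis or stopping rule, that serious events reach the monitor within 24 hours of notification to the investigator, and that full monitoring details are in a charter, which is not among the documents.

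**The concern.** A table by study group is a table by treatment only while each group stays on one treatment. Group B does not. Its cumulative total adds events from two letrozole months to events from up to four placebo months, so the difference between the two groups' totals is smaller than the difference between letrozole and placebo.

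Group A's total has a separate limitation. It is all letrozole during dosing, but it puts events from the first weeks together with events after month 3, and objective 3 asks about the latter.

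Sections 6.1.E and 7.0 describe this as the first trial of letrozole monotherapy beyond 12 weeks in premenopausal women. With one monitor and no stopping rule, the periodic table is the main aggregate view of non-serious effects such as hot flashes, myalgias and fatigue. Cumulative group totals would not show four patterns that the design can reveal: a Group A excess in months 1-2, onset in Group B after its switch to letrozole, resolution in months 5-6, and late onset in Group A.

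**Working it through.** The plan states no adverse-event rate, power or dilution figure, so there is none of its own to reproduce. The check is person-time arithmetic.

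**Inputs.** Group A: letrozole in 6 of 6 months. Group B: letrozole in months 3 and 4 only (both section 3.0). Allocation is 1:1 with 20 women, so 10 per group. Planned enrolment is over 6 months (section 5.1). Assumptions: constant monthly rate L on letrozole and P on placebo, no carry-over, no dropout.

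**Formula.** Over m months of follow-up, of which Group B spends b on letrozole, the expected events per woman are

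- Group A: m × L
- Group B: b × L + (m − b) × P

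The difference is (m − b)(L − P), against a full difference of m(L − P). The fraction lost is b/m, whatever the rates.

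**Cumulative follow-up per woman**

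| Months | b/m | Loss |
|---|---|---|
| 1-2 | 0/2 | 0% |
| 1-3 | 1/3 | 33% |
| 1-4 | 2/4 | 50% |
| 1-5 | 2/5 | 40% |
| 1-6 | 2/6 | 33% |

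Taken as separate periods, months 1-2 and months 5-6 lose nothing. Months 3-4 lose everything, because both groups are on letrozole.

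**Calendar reports.** Reports go out by calendar date while enrolment is staggered. Assume uniform enrolment over 6 months. The loss is then Group B's letrozole time divided by its total follow-up time:

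- Month 3: follow-up runs from 0 to 3 months. Total time is proportional to 3²/2 = 4.5 and letrozole time to 1²/2 = 0.5, so 0.5/4.5 = 11%.
- Month 6: total 6²/2 = 18; letrozole 2²/2 + 2 × 2 = 6; 6/18 = 33%.
- Month 9: total (6² − 3²)/2 + 3 × 6 = 31.5; letrozole 1.5 + 2 × 2 + 3 × 2 = 11.5; 11.5/31.5 = 37%.
- Month 12, all follow-up complete: 33%.

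On the 4-month schedule of section 7.2, the cumulative loss is 25% at month 4, 36% at month 8 and 33% at month 12. If each report covers only the latest interval, the loss is 11%, 41%, 41% and 11% for successive 3-month windows, and 25%, 40% and 25% for 4-month windows.

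**Ratio scale.** With f = b/m, a true rate ratio RR appears as RR/(f × RR + 1 − f). The documents give no rates, so these RR values are assumptions. At f = 1/3, RR 2 appears as 2/(2/3 + 2/3) = 1.50 and RR 3 as 3/(1 + 2/3) = 1.80. At f = 1/2, they appear as 2/1.5 = 1.33 and 3/2 = 1.50. The excess over 1 therefore shrinks by more than the absolute difference does.

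**Women with at least one event.** For assumed monthly risks of 0.10 on letrozole and 0.05 on placebo, over 6 months: Group A 1 − 0.90⁶ = 0.469; Group B 1 − 0.95⁴ × 0.90² = 0.340; placebo throughout 1 − 0.95⁶ = 0.265. The loss is 1 − (0.469 − 0.340)/(0.469 − 0.265) = 37%, close to the person-time figure.

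**What a period table gives.** Each 2-month period holds 10 × 2 = 20 woman-months per group. By treatment taken, the trial has 60 + 20 = 80 letrozole woman-months and 40 placebo woman-months, the latter all in Group B.

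**The case against.** The strongest case against the point is that the documents do not say the monitor sees only pooled totals. Section 8.0 requires presentation by group; it does not exclude a further split. Section 7.2 promises details from the case report form, which may include onset dates, and with 20 women a monitor could read individual records. The charter may contain period tables. This stands: the gap is in what the protocol specifies, and hidden timing cannot be proved.

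A reader might also infer that every letrozole signal is diluted by a third to a half. The documents do not support that:

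- Only Group B mixes drug and placebo.
- Months 1-2 are undiluted.
- Serious events reach the monitor one by one.
- The within-Group-A safety review over months 1-6 is not diluted by placebo time. However, section 10.0 gives it no adverse-event method, and a monitor blinded to group identity may not know which coded group is A.
- Under the uniform-enrolment assumption, none of the calendar reports computed here reaches a loss of one half.

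Finally, no formal test or stopping decision depends on the A-minus-B difference, and the period cells are small. That limits the weight of the point. It does not make cumulative group totals a good summary when data for a better one are already planned.

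**Conclusion.** The point holds for cumulative A-versus-B comparisons of non-serious events. Such totals understate the absolute letrozole-placebo rate difference by one third at 3 or 6 months of follow-up per woman and by one half at 4 months. At calendar reports under uniform 6-month enrolment, the loss is about 11% at month 3, 33% at month 6 and 37% at month 9. These figures assume constant rates, no carry-over and no dropout. On the ratio scale the loss is larger and depends on rates that the documents do not give.

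Group A's totals are not mixed with placebo during dosing, but they do not separate early events from those beyond 3 months. Expedited reporting of serious events is unaffected. If the charter already specifies period tables, a cross-reference in 8.0 is enough for the monitor's reports. In a 20-woman pilot without a formal safety test the practical weight is modest, but the change is worth making because it costs little and serves a stated aim.

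**What to change.** In section 8.0 (and in the charter, if it is silent) and in the final report, specify that:

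- adverse events are tabulated by coded group and by 2-month period of onset: months 1-2, 3-4, 5-6, and the month 7 query separately, with women and woman-months at risk in each cell;
- months 1-2 are the randomised placebo-controlled safety comparison;
- months 3-4 carry a note that both groups are on letrozole, so they hold no drug-placebo contrast;
- any final table by treatment taken at onset is labelled descriptive, because treatment is confounded with period and carry-over.

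Reconcile the 3-month reporting interval in 8.0 with the 4-month interval in 7.2.

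The cost is table programming. The assessment schedule in section 6.1.G already has monthly adverse-event collection through month 7. Section 6.1.E mentions both 2-monthly and monthly assessment, so the case report form should record onset date to place each event in its period. The one downside is that the period pattern may let the monitor guess which coded group is which.
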